### General PK Parameter Rules

- Actual sampling times will be used in the final analyses of individual PK parameters, except for non-bolus pre-dose sampling times which will be set to zero.
- Cmax and tmax will be reported from observed values. If Cmax occurs at more than one timepoint, tmax will be assigned to the first occurrence of Cmax.
- AUC parameters will be calculated using a combination of the linear and logarithmic trapezoidal methods (linear-log trapezoidal rule). The linear trapezoidal method will be applied up to tmax and then the logarithmic trapezoidal method will be used after tmax. The minimum requirement for the calculation of AUC will be the inclusion of at least three consecutive plasma concentrations above the lower limit of quantification (LLOQ), with at least one of these concentrations following Cmax.
- Half-life (t1/2) will be calculated, when appropriate, based on the apparent terminal log-linear portion of the concentration-time curve. The start of the terminal elimination phase for each subject will be defined by visual inspection and generally will be the first point at which there is no systematic deviation from the log-linear decline in plasma concentrations. Half-life will only be calculated when a reliable estimate for this parameter can be obtained comprising of at least 3 data points. If t1/2 is estimated over a time window of less than 2 half-lives, the values will be flagged in the data listings. Any t1/2 value excluded from summary statistics will be documented in the footnote of the summary table.

- A uniform weighting scheme will be used in the regression analysis of the terminal log-linear portion of the concentration-time curve.
- The parameters based on predicted last quantifiable drug concentration ( $C_{last}$ ) will be reported.

### **Individual PK Parameter Rules**

- Only quantifiable concentrations will be used to calculate pharmacokinetic parameters with the exception of special handling of certain concentrations reported below the lower limit of quantification (BQL). Plasma concentrations reported as BQL will be set to a value of zero when all of the following conditions are met:
  - The compound is non-endogenous.
  - The samples are from the initial dose period for a subject or from a subsequent dose period following a suitable wash-out period.
  - The timepoints occur before the first quantifiable concentration.
- All other BQL concentrations that do not meet the above criteria will be set to missing.
- Also, where two or more consecutive concentrations are BQL towards the end of a profile, the profile will be deemed to have terminated and therefore any further quantifiable concentrations will be set to missing for the calculation of the PK parameters unless it is considered to be a true characteristic of the profile of the drug.

### **Individual Concentration vs. Time Profiles**

- Individual concentrations will be plotted utilizing actual sampling times.
- The terminal point selections will be indicated on a semi-logarithmic plot.

### **Average Concentration vs. Time Profiles**

- The average concentration profiles will be graphed using scheduled (nominal) sampling times.
- The average concentration profiles will be graphed using arithmetic average concentrations.
- The pre-dose average concentration for single-dose data from non-endogenous compounds will be set to zero. Otherwise, only quantifiable concentrations will be used to calculate average concentrations.
- Concentrations at a sampling time exceeding the sampling time window specified in the protocol, or  $\pm 10\%$ , will be excluded from the average concentration profiles.

- Concentrations excluded from the mean calculation will be documented in the final study report.
- A concentration average will be plotted for a given sampling time only if 2/3 of the individual data at the timepoint have quantifiable measurements that are within the sampling time window specified in the protocol or  $\pm 10\%$ . An average concentration estimated with less than 2/3 but more than 3 data points may be displayed on the mean concentration plot if determined to be appropriate and will be documented within the final study report.

### **Treatment of Outliers during Pharmacokinetic Analysis**

Application of this procedure to all pharmacokinetic analyses is not a requirement. Rather, this procedure provides justification for exclusion of data when scientifically appropriate. This procedure describes the methodology for identifying an individual value as an outlier for potential exclusion, but does not require that the value be excluded from analysis. The following methodology will not be used to exclude complete profiles from analysis.

#### Data within an Individual Profile

A value within an individual profile may be excluded from analysis if any of the following criteria are met:

- For pharmacokinetic profiles during single dosing of non-endogenous compounds, the concentration in a pre-dose sample is quantifiable.
- For any questionable datum that does not satisfy the above criteria, the profile will be evaluated and results reported with and without the suspected datum.

#### Data between Individual Profiles

1. If  $n < 6$ , then the dataset is too small to conduct a reliable range test. Data will be analyzed with and without the atypical value, and both sets of results will be reported.
2. If  $n \geq 6$ , then an objective outlier test will be used to compare the atypical value to other values included in that calculation:
  - a. Transform all values in the calculation to the logarithmic domain.
  - b. Find the most extreme value from the arithmetic mean of the log transformed values and exclude that value from the dataset.
  - c. Calculate the lower and upper bounds of the range defined by the arithmetic mean  $\pm 3 \times \text{SD}$  of the remaining log-transformed values.
  - d. If the extreme value is within the range of arithmetic mean  $\pm 3 \times \text{SD}$ , then it is not an outlier and will be retained in the dataset.

---

- e. If the extreme value is outside the range of arithmetic mean  $\pm 3*SD$ , then it is an outlier and will be excluded from analysis.

If the remaining dataset contains another atypical datum suspected to be an outlier and  $n \geq 6$  following the exclusion, then repeat step 2 above. This evaluation may be repeated as many times as necessary, excluding only one suspected outlier in each iteration, until all data remaining in the dataset fall within the range of arithmetic mean  $\pm 3*SD$  of the log-transformed values.

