## 7. SAMPLE SIZE JUSTIFICATION

The sample size for the study was chosen to provide sufficient data to evaluate the primary objective of this study and is not intended to achieve any priori statistical requirements.

Approximately 24 Chinese patients with T2DM may be enrolled so that approximately 16 patients complete the study with compliant defined dosing regimen. Patients will be administered either 16 (Cohort 1) or 24 (Cohort 2) weekly SC doses of tirzepatide or placebo in a ratio of 10 tirzepatide:2 placebo for both cohorts.

Replacement of discontinued patients is not planned because the sample size is determined considering the expected drop-out rate.

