#### Reporting of Excluded Values

Individual values excluded as outliers will be documented in the final report. Approval of the final report will connote approval of the exclusion.

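### The SAP's fixed 3-SD leave-one-out outlier rule would flag a valid PK value in about 22% of clean datasets at n = 10 and 27–31% at n = 6–7, and no all-data summary is required when a flagged value is dropped

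*SAP*

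**What the plan says.** SAP 9.3.1 has an outlier procedure for PK data. For values compared between profiles with n of 6 or more, all values are log-transformed and the first instruction is "Find the most extreme value from the arithmetic mean of the log transformed values and exclude that value from the dataset". Bounds are then set at the mean ± 3 SD "of the remaining log-transformed values". If the extreme value is outside the bounds, "then it is an outlier and will be excluded from analysis". The step may be repeated, one value at a time, while at least 6 values remain. The multiplier is 3 at every n, and no error rate is given.

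The introduction to the procedure (Treatment of Outliers during Pharmacokinetic Analysis) is softer. It does not require the procedure in every analysis, and it says that identifying a value as an outlier "does not require that the value be excluded from analysis". It also rules out dropping complete profiles.

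Reporting differs by situation:

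- Questionable value within one profile: "the profile will be evaluated and results reported with and without the suspected datum".
- Between profiles, n below 6: "Data will be analyzed with and without the atypical value, and both sets of results will be reported".
- Between profiles, n of 6 or more: no second set of results. Reporting of Excluded Values asks only that exclusions be documented, and adds: "Approval of the final report will connote approval of the exclusion".

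**The concern.** The value tested is always the most extreme one in the set, and it is left out of the SD it is judged against. In a small sample that SD is imprecise and tends to be low, because the value that would have widened it has gone. A fixed limit of 3 therefore does not mark a rare event at n = 6 to 10. This arises at the first pass; repetition only adds further removals.

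AUC and Cmax are the secondary endpoint (Protocol, Table GPHT.1) and are reported descriptively, so the geometric mean and geometric CV are the result that readers will use. If flags are acted on, valid AUC or Cmax values leave the summary and between-patient variability is understated. The SAP's protection against this, reporting both ways, is absent where the test operates, and n of 6 or more is the expected case here.

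**Working it through.** The documents state no error rate for this test, so there is no planned figure to reproduce.

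**Inputs**

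- Rule: SAP 9.3.1, Data between Individual Profiles, step 2.
- Distribution: log-normal, as SAP 9.1 assumes for AUC and Cmax. A clean dataset is therefore a normal sample on the log scale with no true outlier.
- Size of a summary cell: PK parameters are summarized by treatment and profile day (SAP 9.3.2), with separate labels per cohort (SAP 6). Each cohort has 10 tirzepatide patients (SAP 7), and placebo samples are not planned for assay (Protocol 9.5.1). A cell therefore starts at n = 10.
- Size after dropout: SAP 7 has 24 "enrolled so that approximately 16 patients complete the study with compliant defined dosing regimen". With even dropout, 10 × 16/24 = 6.7 tirzepatide patients per cohort.

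**First-pass flag rate**

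For a given value, the deviation from the mean of the others, divided by their SD × √(1 + 1/(n−1)), follows a t distribution with n−2 degrees of freedom. The chance that it exceeds the limit is 2 × P(t > 3/√(1 + 1/(n−1))). Multiplying by n gives the rate per dataset; the simulation shows that overlap between values is negligible.

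| n | 3/√(1 + 1/(n−1)) | per value | × n | simulated |
|---|---|---|---|---|
| 6 | 2.74 | 5.20% | 31.2% | 31.2% |
| 7 | 2.78 | 3.90% | 27.3% | 27.3% |
| 8 | 2.81 | 3.09% | 24.7% | 24.7% |
| 10 | 2.85 | 2.16% | 21.6% | 21.6% |

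The simulation applied step 2 to 1,000,000 clean datasets per n. Flag rates do not depend on the CV. Two or more values are removed in 8.5% of sets at n = 7, 6.7% at n = 8 and 5.0% at n = 10. At n = 6 the rule stops after one removal.

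The cause is the leave-one-out SD. If the 3 SD came from the full sample, no value could be flagged at n ≤ 10, because the largest possible deviation is (n−1)/√n SDs, which is 2.85 at n = 10.

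**Effect on the reported geometric CV**

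The true CV of 25% is an assumption; the documents give none. It corresponds to a log SD of √ln(1 + 0.25²) = 0.246.

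| n | flagged sets: before | one removal | full iteration | all sets: before | every flag deleted |
|---|---|---|---|---|---|
| 6 | 23.9% | 12.6% | 12.6% | 23.9% | 20.3% |
| 7 | 24.0% | 13.7% | 11.7% | 24.0% | 20.7% |
| 8 | 24.2% | 14.7% | 12.7% | 24.2% | 21.3% |
| 10 | 24.4% | 16.1% | 14.5% | 24.4% | 22.2% |

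Over a range of true CVs at n = 10, the all-set average falls from 14.6% to 13.3% (true CV 15%) and from 39.1% to 35.6% (true CV 40%). In flagged sets the geometric mean also moves, in either direction, by about 6% at n = 10 and 7–8% at n = 7; under this symmetric model it has no systematic bias.

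**Limits that would hold a chosen rate**

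For a 5% rate per dataset (my choice), the limit is t(1 − 0.05/(2n), n−2) × √(1 + 1/(n−1)): 5.31, 4.73, 4.40 and 4.04 SDs at n = 6, 7, 8 and 10.

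**The case against.** The strongest reply is that the SAP does not plan to screen every dataset. The procedure is optional, is meant for a value that already looks atypical, and supports exclusion only when scientifically appropriate. The 22–31% is therefore not the expected deletion rate in this study, which cannot be known from the documents. That stands, and the figures should be read as upper limits. It does not repair the rule: the SAP offers the test as justification for exclusion and calls it objective, yet it fires in a fifth to a third of clean sets. Choosing where to apply it after seeing the data adds selection.

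Second, n = 6–7 is a low-end case. The 16 are patients who complete everything, including follow-up, with compliant dosing, while the PK population needs only one dose and evaluable data. More than 6.7 per cohort may contribute a last profile, and Days 1 and 50 should be nearer 10. This also stands, but the rate at n = 10 is still 22%.

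Third, exclusions are traceable: they must be documented, special handling must be described, and all data are listed. With at most 10 values per cell a reader could rebuild the full summary, and the separate table shells, which are not available, might contain one. This limits the harm. But the SAP text does not oblige the sponsor to report that summary.

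Fourth, the split can be defended as design: both results where there is no objective test, the test where there is one. That would be sound only if the test were reliable at these sizes. Finally, the 5% target and the bar on iteration are preferences, and the main fix does not depend on them.

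**Conclusion.** The concern holds. On clean log-normal data with every set tested, the rule flags at least one valid value in 31%, 27%, 25% and 22% of sets at n = 6, 7, 8 and 10. Acting on every flag would lower the average reported geometric CV by about 2 percentage points at n = 10 and 3 at n = 7 (true CV 25% assumed), with much larger falls in the sets affected. The flag rates rest on log-normality and the absence of true outliers; n = 6–7 also rests on even dropout. Because use is discretionary, these are ceilings, not forecasts.

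Two drafting faults stand regardless of the arithmetic. The introduction makes exclusion optional while the step makes it automatic, and the with-and-without requirement lapses at n of 6 or more. The change should be made, but it is not critical: PK is a descriptive secondary endpoint, exclusions are traceable, and the primary safety analysis is unaffected.

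**What to change.** 1. Reconcile the introduction to the outlier procedure with the exclusion step, so that the SAP states once whether a flagged value is removed.
2. Extend the existing with-and-without rule to every n. The all-data summary is the main PK result, and a second summary omits the flagged value.
3. Allow exclusion from the main result only for a documented dosing, sampling or assay cause.
4. If a statistical screen is kept, use it only as a flag, without iteration and with limits that depend on n. For a 5% rate per dataset these are about 5.3, 4.7, 4.4 and 4.0 leave-one-out SDs at n = 6, 7, 8 and 10. The sponsor may choose another rate, but should state it.

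The cost is SAP wording and at most one duplicate row in the PK summary tables. Reported CVs may be somewhat larger.

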#### Reporting of Excluded Values

Individual values excluded as outliers will be documented in the final report. Approval of the final report will connote approval of the exclusion.

### **9.3.2 Pharmacokinetic Statistical Methodology**

All PK parameters will be summarized by treatment and PK profile day, and listed.

Trough concentrations will be summarized by cohort and timepoint, and listed.

### **9.4 Pharmacodynamic Assessments**

#### **9.4.1 Lipids Assessment**

Total cholesterol, high-density lipoprotein cholesterol, low-density lipoprotein cholesterol, and triglycerides data will be listed and summarized by treatment and timepoint. Changes from baseline will be presented, where baseline is defined as the Day 1 predose assessment.

#### **9.4.2 Meal Intake and Appetite**

The subjective rating of appetite sensations is measured using a 100-mm visual analogue scale (VAS) for parameters of hunger, fullness, satiety, and prospective food consumption before and 4 to 5 hours after the standardized lunch and dinner meals.

Overall appetite score is calculated as the average of the 4 individual scores – satiety + fullness + (100-prospective food consumption) + (100-hunger) / 4. The higher overall appetite score indicates less appetite, and the lower score indicates more appetite.

The data will be listed and summarized by treatment and timepoint. Changes from the assessment before food consumption will also be presented.

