**Table GPHT.1. Objectives and Endpoints**

Primary Objectives	Endpoints
To investigate the safety and tolerability of tirzepatide after multiple SC doses administered to Chinese patients with T2DM	Incidence of TEAEs
Secondary Objectives	Endpoints
To characterize the PK of tirzepatide after multiple SC doses in Chinese patients with T2DM	AUC and $C_{\max}$ of tirzepatide
Exploratory Objectives	Endpoints
To investigate the efficacy of tirzepatide after multiple SC doses administered to Chinese patients with T2DM	Hemoglobin A1c, body weight, fasting plasma glucose levels, 7p-SMPG
To investigate the exploratory PD effects of tirzepatide after multiple SC doses administered to Chinese patients with T2DM	Lipids, subjective appetite sensation (VAS)
To evaluate the formation of ADAs to tirzepatide after multiple SC doses administered to Chinese patients with T2DM	Presence of ADAs to tirzepatide

[figure not shown]
Abbreviations: ADA = antidrug antibody; AUC = area under the concentration-time curve;  $C_{\max}$  = maximum observed drug concentration; PD = pharmacodynamic; PK = pharmacokinetics; SC = subcutaneous; 7p-SMPG = 7-point self-monitored plasma glucose; T2DM = type 2 diabetes mellitus; VAS = visual analogue scale.

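### The printed overall appetite score expression lacks outer brackets; if coded literally, it would run from 0 to 325 and give hunger a quarter of the weight of each other item

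*SAP*

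**What the plan says.** SAP 9.4.2 (Meal Intake and Appetite) says that appetite sensations are "measured using a 100-mm visual analogue scale (VAS) for parameters of hunger, fullness, satiety, and prospective food consumption", rated before and again some hours after standardized lunches and dinners. It then defines the composite: "Overall appetite score is calculated as the average of the 4 individual scores", followed after a dash by "satiety + fullness + (100-prospective food consumption) + (100-hunger) / 4". On direction it says: "The higher overall appetite score indicates less appetite, and the lower score indicates more appetite". The section plans listings, descriptive summaries for each treatment at each timepoint, and changes from the rating taken before the meal.

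Protocol 9.6.2 carries the same words and the same expression. Table GPHT.1 of the Protocol places subjective appetite (VAS) among the exploratory pharmacodynamic endpoints. Neither document prints a bracketed version, a numerical range for the composite or a worked example.

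**The concern.** The words and the expression in one sentence do not agree. The two reversed items have brackets but the sum of four terms does not, so the division by 4 applies to the last term alone. A programmer who types the expression as printed would derive a different variable from the one described.

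Two features make this easy to miss. The statement about direction is true under both readings, so it would not expose a literal derivation. The Protocol and the SAP carry the identical expression, so checking one against the other would not reveal it, and SAP section 11 declares no changes from the Protocol. At stake are the listings, summaries and pre-meal to post-meal changes for the only composite that the documents define from the appetite ratings.

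**Working it through.** The documents give no figure for this score, so there is none to reproduce. The check compares the printed expression with the mean that the words require.

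**Inputs.** Satiety S, fullness F, prospective food consumption P and hunger H are each rated from 0 to 100 mm (SAP 9.4.2, Protocol 9.6.2).

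**Two readings.**
- Literal: L = S + F + (100 − P) + (100 − H)/4
- Average: A = [S + F + (100 − P) + (100 − H)]/4

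They are linked by L = 4A − 0.75 × (100 − H). Because the second term varies with hunger, no constant converts one score to the other.

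**Range and midpoint.**
- Minimum: 0 under both readings (S = F = 0, P = H = 100).
- Maximum (S = F = 100, P = H = 0): L = 100 + 100 + 100 + 25 = 325; A = 400/4 = 100.
- All ratings at 50: L = 50 + 50 + 50 + 12.5 = 162.5; A = 200/4 = 50.

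**Weights.** In L the weights are 1 : 1 : 1 : 0.25, so hunger carries 0.25/3.25 = 7.7%. In A it carries 1/4 = 25%. A 20-mm rise in fullness adds 20 to L and 5 to A. A 20-mm fall in hunger adds 5 to both.

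**Example profiles.**

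| Profile | S | F | P | H | L | A |
|---|---|---|---|---|---|---|
| a | 60 | 60 | 40 | 80 | 60 + 60 + 60 + 5 = 185 | 200/4 = 50 |
| b | 40 | 40 | 60 | 20 | 40 + 40 + 40 + 20 = 140 | 200/4 = 50 |
| c | 40 | 40 | 60 | 0 | 40 + 40 + 40 + 25 = 145 | 220/4 = 55 |
| d | 45 | 45 | 55 | 60 | 45 + 45 + 45 + 10 = 145 | 175/4 = 43.75 |

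Profiles a and b are equal on A but differ by 45 on L. Profiles c and d are equal on L but differ by 11.25 on A. Profiles a and c change order: a is higher on L (185 against 145) and c is higher on A (55 against 50).

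**How far the two would diverge across patients.** The documents give no item correlations. Assume equal item variances and a common correlation r between items after hunger and prospective consumption are reversed:

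| r (assumed) | Hunger's share of the variance of L | Correlation of L with A |
|---|---|---|
| 0 | 2.0% | 0.929 |
| 0.3 | 5.4% | 0.972 |
| 0.5 | 6.4% | 0.984 |
| 0.7 | 7.1% | 0.992 |
| 0.9 | 7.5% | 0.998 |

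Hunger's share of the variance of A is 25% throughout. The change of scale would be large and the re-ordering of patients limited, and smaller the more closely the items move together.

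**The case against.** The strongest reply is that the sentence settles its own meaning. The expression comes after a dash, as a gloss on the word average, and an average of four 100-mm ratings cannot exceed 100. On that view there is one definition and one slip of notation, and a literal derivation is speculation: the TFL shells and programs are not available here. Even if it happened, a mean above 100 would be conspicuous, and because SAP 9.1 requires listings of all databased data, the score could be re-derived from the four ratings.

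Most of this stands. The intent is clear, and the 0 to 100 range can be inferred from the item scale even though neither document states it. What the reply does not remove is that the printed expression is wrong as a derivation rule. Nor are very large values guaranteed to appear: L can fall below 100 for patients with strong appetite, so a quick look at individual values could miss it.

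A reader might also infer three stronger things, none of which the documents support:
- That the expression overrides the words. Nothing in either document ranks one above the other.
- That hunger would be all but ignored. It would be cut to a quarter of the weight of each other item, but not removed.
- That a treatment comparison would be biased. Protocol 10.3.4 and SAP 9.4.2 plan only listings and descriptive summaries of appetite, with no inferential contrast.

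**Conclusion.** The printed expression is wrong in both documents, by a missing pair of brackets. If coded literally, it would give a score from 0 to 325 instead of 0 to 100, with hunger at 7.7% of the weight instead of 25%, and would distort the descriptive summaries of this composite. If the programmer follows the words, the effect is zero, and the documents do not show which was done.

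The range and the weights follow from the expression and the 100-mm scale alone. Only the variance shares and the correlations of 0.929 to 0.998 rest on the assumed equal variances and common item correlation.

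The consequence is confined to an exploratory measure. Neither the primary safety endpoint nor the secondary pharmacokinetic endpoints use it. The sample size does not rest on it either: SAP section 7 says that the size "is not intended to achieve any priori statistical requirements". This is a small correction, worth making because it is specific and costs almost nothing.

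**What to change.** In SAP 9.4.2 and any TFL specification, print the score as [S + F + (100 − P) + (100 − H)] / 4, with the item names written out, and state that it ranges from 0 to 100. Correct Protocol 9.6.2 in the same way at the next amendment.

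Use the range as a programming check: any value above 100 shows that the sum was not bracketed. Because a literal score can also fall below 100, add one test record with all four ratings at 50, which must return 50 and not 162.5.

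The cost is one pair of brackets and a range statement in each place. No new data are needed. If the score has already been programmed from the expression as printed, it can be re-derived from the four ratings.
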